## D. PROTECTION OF HUMAN SUBJECTS

### Risk/Benefit Assessment

The main study procedures include a medication trial, clinical evaluation, MRI, blood draw (with a volume to be collected < 50mL), and completion of questionnaires. The primary risks of the study are a) adverse effects of study medications, b) emotional distress, c) incidental findings, and d) loss of confidentiality.

1. Interview and psychiatric emergencies. Subjects may experience discomfort during the clinical interview and evaluations when discussing symptoms, life events, and social support. The Research Coordinator and Specialists will be experienced and skilled in interviewing subjects. Should the subject wish to stop or take a break, they will allow it. In addition, should the subject express any physical or psychological symptoms that are concerning or possibly represent an emergency, the study physician ([name]) or other approved study clinician will be contacted immediately to assess the subject and to

determine the appropriate course of action. Possible situations where this would occur include but are not limited to thoughts of suicide, homicidal or violent thoughts, psychosis, or a change in the subject's physical status if they start feeling bad or complaining of new physical symptoms (such as chest pain, acute nausea, etc.). Importantly, the Research Coordinator/Specialist is not the only individual screening for such potential emergencies. These domains will be independently assessed by [name]/PA-C during the health and physical exam and any subsequent future clinical interview. Options for addressing such emergencies may include contacting the individual's mental health caregiver, referring for urgent evaluation and treatment, or emergent hospitalization.

2. Study Medication. The varenicline package insert details adverse events associated with the medication. Specifically, it reports that "the most common adverse reactions (>5% and twice the rate seen in placebo-treated patients) were nausea, abnormal (e.g., vivid, unusual, or strange) dreams, constipation, flatulence, and vomiting." Meta-analyses of the four main adverse events in varenicline versus placebo groups in adult trials yielded relative risks (RRs) of 3.21 (95% CI 2.71, 3.80) for nausea, 1.50 (95% CI 1.26, 1.79) for insomnia, 2.79 (95% CI 2.09, 3.72) for abnormal dreams, and 1.20 (95% CI 1.00, 1.45) for headache [16]. While post-marketing anecdotal reports of psychiatric adverse events led to an FDA "black box" warning for varenicline, a reanalysis of controlled trials revealed no evidence that varenicline is associated with neuropsychiatric adverse events [17].

N-acetylcysteine (NAC) has a long-established safety record in adults and children, with FDA approval since 1963. A meta-analysis of studies evaluating long-term oral treatment with NAC for prevention of chronic bronchitis found that NAC was well tolerated, with generally mild, most commonly gastrointestinal adverse effects that did not require treatment interruption [18].

The informed consent process will be used to thoroughly educate participants about potential medication-related risks. Rigorous screening procedures and strict exclusion criteria are designed to exclude potential participants at elevated risk for adverse events. This includes comprehensive medical and psychiatric assessment and evaluation. The study physician (board certified psychiatrist), or the physician assistant under his direct supervision, will conduct serial medication management sessions weekly throughout treatment, providing comprehensive, detailed adverse event monitoring. Participants will have access to the study medical clinician 24 hours, 7 days a week for emergencies. Participants experiencing intolerable adverse events will have the opportunity to reduce dose or discontinue medication altogether, while remaining in the study for ongoing monitoring. The study physician has full admitting privileges at the Medical University of South Carolina, in the event that symptom acuity warrants intensive intervention. Urine pregnancy tests will be conducted serially throughout treatment for female participants.

3. Magnetic Resonance Imaging. Although this procedure is generally low-risk, there are particular concerns. Individuals will be screened for the presence of implanted metal (including but not limited to medical devices, shrapnel, tattoos or permanent makeup); those

who screen positive will be excluded from the study. Some participants may feel uncomfortable or confined once positioned within the bore of the MRI system. This potential reaction is reduced by discussing the procedure prior to entry into the magnet room and by communicating with the subject regularly over the intercom. Most importantly, participants will be exposed to the scanning environment through the use of both a mock scanner and a scanner simulator. During the MRI, subjects will have voice contact with a radiology technician, and may request the scan be stopped at any time. If a participant feels uncomfortable in the scanner, the imaging procedure is terminated and the participant is removed from the magnet.

4. **Incidental Findings: Magnetic Resonance Imaging:** Another risk is the occurrence of incidental findings on MRI, such as risk of previously unrecognized stroke, hematomas, or other findings. All scans are reviewed at time of acquisition. Should any concerning findings be seen, we will obtain a consultation from a clinical neuroradiologist who will provide an opinion on the significance of the finding and recommendations for further evaluation. [name] will contact the subject in question, convey these findings and recommendations, and facilitate referrals for further evaluation and treatment as needed.
5. **Incidental Findings: Medical Evaluations:** It is possible that subjects will present with vital sign irregularities needing further evaluation. With the subject's permission, such results will be shared with each subject's treating physician. For urgent findings, such as substantially elevated blood pressure, study staff will contact [name] or another approved study clinician, who will evaluate the subject as needed and make recommendations for what further assessment is needed. Possible options include referral to the subject's treating provider or other urgent or emergent evaluation.
6. **Phlebotomy:** Subjects will have blood drawn by experienced phlebotomists in the TRAIN Laboratory. Every effort is made to minimize risks, which include hematoma, infection, fainting, and excess blood loss. Sterile technique is used to minimize infection risk, and subjects are asked to apply a pressure with a gauze pad to prevent excess bleeding.
7. **Breach of confidentiality:** There is the potential risk of breach of confidentiality of clinical and laboratory information. [name] has experience as an investigator dealing with such sensitive information and has experience assuring that data is adequately protected. Safeguards to protect confidentiality include locked records and firewalls around password-protected electronic data, and all study data being coded, with the key linking the code with a subject's identity being kept in a separate, locked file. Participants' initials will also be present on some questionnaires; however, the questionnaires containing the initials will be stored in a locked file cabinet. Video clips will be stored on a password protected server and viewed by only approved research staff.

Similar safeguards are followed for storage and processing of MRI data. MRI data is stored on secure storage owned by the Center for Biomedical Imaging (CBI). CBI has a longstanding policy of reviewing all scans that are transferred to the laboratory from the MRI scanners, and

assuring that all subject identifiers are removed, both from the scan image itself but also the electronic headers of the scan. The MRI scans are identified only by subject code, study code, and date of acquisition.

#### Potential Benefits

Participants in the study, regardless of randomization group, will benefit by receiving a) comprehensive medical and psychiatric evaluation, and b) weekly smoking cessation medication management visits with the study medical clinician throughout active treatment.

#### Importance of the Knowledge to be Gained

The overall benefit is an increase in our understanding of the neurobiological mechanisms underlying nicotine addiction and the novel combination of NAC+VRN for treating nicotine addiction. This will help us better understand the pathophysiology of smoking and provide valuable information guiding subsequent clinical trials.

#### Targeted Enrollment Table

TARGETED/PLANNED ENROLLMENT: Number of Subjects			
Ethnic Category	Sex/Gender		
	Females	Males	Total
Hispanic or Latino	5	5	10
Not Hispanic or Latino	70	70	140
Ethnic Category: Total of All Subjects *	75	75	150
Racial Categories			
American Indian/Alaska Native	0	0	0
Asian	2	2	4
Native Hawaiian or Other Pacific Islander	0	0	0
Black or African American	25	25	50
White	48	48	96
Racial Categories: Total of All Subjects *	75	75	150

### 1. SUMMARY OF PROTOCOL

#### a. *Brief Description of Protocol (Study Design)*

This study will examine the effects of combining Varenicline (VRN) and *N*-acetylcysteine (NAC) on neural circuitry function and treating nicotine addiction. Healthy adult nicotine dependent cigarette smokers interested in quitting (n=150) will be randomized to one of four PBO-controlled conditions for 4 weeks: 1) VRN+NAC, 2) VRN+PBO, 3) NAC+PBO or 4) PBO+PBO. Following a baseline fMRI (Day 0) and 1 week of medication, participants will be contingently reinforced for 3 days of smoking abstinence and be fMRI scanned (fMRI-2/Day 10) while nicotine deprived during a resting state and a cue-reactivity (CR) task. Participants will be followed over the next 3 weeks of treatment and clinical variables will be assessed.

#### b. **Specific Aims**

*Aim 1.* Identify the effects of *N*-acetylcysteine (NAC) + Varenicline (VRN) on resting neural network function and behavior. We will examine the individual and combined effects of VRN and NAC on neural circuitry function in humans. We will also identify relations between neural circuitry function and nicotine/smoking self-administration, withdrawal symptom severity and the maintenance of smoking abstinence over the duration of the study.

*Aim 2.* Examine the effects of NAC+VRN on drug-cue brain response and behavior. We will examine the individual and combined effects of VRN and NAC on cue-induced brain response and behavior in humans, focusing on limbic-striatal and corticostriatal networks. In these experiments we will also identify relations between neural circuitry function and nicotine/smoking self-administration and withdrawal symptom severity and the maintenance of smoking abstinence over the duration of the study.

*Exploratory Aim:* Participants will complete a Smoking Regulation Relapse task (SRRT) in the laboratory—the effects of VRN+NAC on smoking topography during the SRRT, and on subsequent smoking behavior and relapse will be examined. Whole brain fMRI analyses will be conducted, and relations between fMRI measures and clinical outcomes will be examined.

#### c. **Inclusion/Exclusion Criteria**

##### Inclusion Criteria all subjects:

1. Age 18 - 65
2. English fluency as demonstrated in providing informed consent and the ability to independently follow directions in completing assigned assessments and tasks
3. Functional vision (with corrective lenses as needed) to complete assigned assessments and tasks
4. Current nicotine dependent cigarette smoker with a minimum smoking history of two years
5. Interest in quitting smoking or contemplating a quit attempt in the next 6 months

6. If female, agreement to use birth control (any form of hormonal contraception such as Depo-Provera, daily oral contraception, transdermal patch, or Nuva-ring; intrauterine device; sterilization; or double barrier contraception, which is a combination of any two of the following methods: condoms, spermicide, diaphragm) to avoid pregnancy
7. Refrain from all other tobacco (i.e. dip/chew, cigars, cigarillos) and/or nicotine products (e-cigs, patches, gum, inhalers/sprays) for the duration of study participation

**Exclusion Criteria all subjects:**

1. Past head injury or primary neurological disorder associated with MRI abnormalities, including dementia, MCI, brain tumors, epilepsy, Parkinson's disease, or demyelinating diseases
2. Any physical or intellectual disability affecting completion of assessments
3. Any contraindication to MRI
4. Positive urine drug screen for illicit substances (other than marijuana or cocaine).  
4a. For those testing positive for marijuana and/or cocaine, meet dependence criteria
5. Current or past psychosis
6. ECT in last 6 months
7. Use of antidepressants, medications with smoking cessation efficacy, or other psychotropic medications in the last month.
8. Positive urine pregnancy test or current breast feeding status
9. Any other condition or concern that in the Investigator's opinion would impact participant safety, compliance with study instructions, or potentially confound the interpretation of the study results

As part of exclusion criteria #9, participants are specifically asked to not take part in any other research during their active participation in the protocol once eligibility at screening is made through the last visit day of the protocol.

Among females, pregnancy at screening will be exclusionary. Females of childbearing potential must agree to undergo a pregnancy test before the medication trial and prior to each fMRI scanning session. They must further agree to notify the study physician or PA if they become pregnant during the study.

**d. Power Calculation and Sample Size**

Our primary aim is to evaluate the effects of VRN+NAC on fMRI BOLD signal. We have investigated multiple components of these effects in previous studies: Effects of smoking on cue-reactivity: In a previous study, smoking abstinence increased activation in dlPFC to visual cues in smokers with low negative affect ( $d = .65$ ); the opposite pattern was observed among smokers with elevated negative affect ( $d = -1$ ) which resulted in a significant smoking state by negative affect group interaction ( $d = 1.5$ ). Effects of smoking abstinence on resting-state functional connectivity: Smoking abstinence strengthened rsFC in an amygdala-striatal circuit ( $rZ$ 's between .56 and .91) and weakened rsFC in the corticostriatal network ( $rZ = .71$ ). Effects of NAC on rsFC: In our ongoing PBO-controlled NAC fMRI pilot study (N=20), we find that as compared to the PBO group, smokers in the NAC group exhibit stronger rsFC in the

corticostriatal network ( $r_s = .79$ ). Whereas we have not specifically assessed the interactive effects of NAC +VRN on brain function, the studies listed above provide strong support that we will observe significant effects in a sample of 100 participants. The effects of NAC+VRN on neural network function (Aim 1) and brain CR (Aim 2) will be assessed. If we assume that as with our studies of smoking abstinence and NAC, these effects are of medium to large size (e.g.  $d = .8$ ), with alpha =.05 (1-tailed), a sample of 25 participants in each treatment group will result in power  $>.90$  for detecting effects of treatment on rsFC and CR-BOLD response. In sum, we are confident that the proposed sample size of 100 will be sufficient to test Aims 1a and 2a.

*Exploratory Clinical Outcomes.* The clinical outcomes assessed in this study are designed to assess relapse for 3 weeks following a period of monitored abstinence under PBO-controlled medication conditions. Although the study is not specifically powered to detect the secondary hypothesis of an additive effect of VAR and NAC on abstinence from nicotine (2x2 interaction), the stated sample size will allow for the estimation of effect sizes and the precision of the variance in order to inform a subsequent larger study. Based upon completion rates in our prior studies, we anticipate a 15% attrition rate between randomization and the end of the clinical portion of the study; thus, we anticipate that 94 of the 150 randomized participants will provide secondary clinical data for analysis (23 in each treatment assignment). Assuming that no additive effect is present and that the NAC/PBO abstinence rate is 10%, we will have 80% power with a type 1 error rate of 5% to detect an abstinence rate of 33% in the VRN group.

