### **A. Summary of Protocol**

#### *a. Brief Description of Protocol (Study Design)*

This study will examine the effects of combining Varenicline (VRN) and *N*-acetylcysteine (NAC) on neural circuitry function and treating nicotine addiction. Healthy adult nicotine dependent cigarette smokers interested in quitting (n=150) will be randomized to one of four PBO-controlled conditions for 4 weeks: 1) VRN+NAC, 2) VRN+PBO, 3) NAC+PBO or 4) PBO+PBO. Following 1 week of medication, participants will be contingently reinforced for 3 days of smoking abstinence and be scanned using functional magnetic resonance imaging (fMRI) techniques, while nicotine deprived during a resting state and a cue-reactivity (CR) task. Participants will be followed over the next 3 weeks of treatment and clinical variables will be assessed.

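### Exploratory clinical outcomes: 15% attrition from 150 randomized leaves about 127 participants with data, not the stated 94, which would be a 37% loss

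*Combined protocol and SAP*

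**What the plan says.** The figures are in the exploratory clinical outcomes paragraph of section 1.d (Power Calculation and Sample Size).

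- Attrition: "we anticipate a 15% attrition rate between randomization and the end of the clinical portion of the study".
- Number with data, presented as following from that rate: "we anticipate that 94 of the 150 randomized participants will provide secondary clinical data for analysis (23 in each treatment assignment".
- Power: "Assuming that no additive effect is present and that the NAC/PBO abstinence rate is 10" percent, "we will have 80% power with a type 1 error rate of 5% to detect an abstinence rate of 33% in the VRN group".
- Status of the outcome: "the study is not specifically powered to detect the secondary hypothesis of an additive effect". The data are meant to give effect sizes and variances for a later, larger study.

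Both brief descriptions of the design (sections A.a and 1.a) confirm the number randomized: "interested in quitting (n=150) will be randomized to one of four PBO-controlled conditions for 4 weeks". The Targeted Enrollment Table also totals 150. Section C, under participant recruitment and selection, plans to enrol 150 in order to obtain 100 complete datasets, and does not define what makes a dataset complete.

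**The concern.** The paragraph gives the base (150 randomized), the interval (randomization to the end of the clinical portion) and the rate (15%), then offers 94 as the result. It is not the result of those inputs. The gap is about 33 participants, which is too large for rounding, and no section describes a further loss between 127 and 94.

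A reader therefore cannot tell whether about 94 or about 127 participants are expected to inform the clinical estimates, whether observed retention should be judged against 15% or 37%, or which sample the power sentence describes. The data are intended to inform a larger study, so the expected precision depends on the answer.

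**Working it through.** **Inputs.** From section 1.d: 150 randomized, 15% attrition, 94 with data, 23 per arm, 10% v 33% abstinence, 5% type 1 error, 80% power. From section C: 150 enrolled, 100 complete datasets. Equal allocation to four arms is assumed; the equal numbers per arm imply it, but no ratio is stated.

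**Step 1: try to reproduce 94.** Retained = randomized × (1 − attrition).

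- 150 × 0.85 = 127.5; ÷ 4 = 31.9 per arm. The stated figures are 94 and 23.
- Dividing instead: 150 / 1.15 = 130.4.
- Loss applied twice: 150 × 0.85² = 108.4. Three times: 150 × 0.85³ = 92.1, which comes near 94, but nothing in the text supports three successive losses.
- 15% applied to the 100 complete datasets: 100 × 0.85 = 85.

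No reading with a basis in the text gives 94. The per-arm figure is also slightly loose: 4 × 23 = 92, and 94 / 4 = 23.5.

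**Step 2: what each figure implies about the others.**

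| Figures taken as right | Implied third figure |
|---|---|
| 150 and 15% | 127.5 with data, about 32 per arm |
| 150 and 94 | attrition 1 − 94/150 = 37.3% |
| 15% and 94 | 94 / 0.85 = 110.6, so about 110 or 111 randomized |

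Section C implies 1 − 100/150 = 33.3%, which is neither 15% nor 37.3%.

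**Step 3: which sample does the power sentence fit?** For n per group, with p₁ = 0.10, p₂ = 0.33 and p̄ = 0.215, the pooled-variance z-test gives

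power = Φ{[0.23 − 1.96 √(2 p̄(1 − p̄)/n)] / √[(p₁(1 − p₁) + p₂(1 − p₂))/n]}.

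- n = 47 (94 split by varenicline yes/no): (0.23 − 0.1661) / 0.0814 = 0.785, so power is 0.784.
- n = 64 (about 127 split the same way): (0.23 − 0.1423) / 0.0697 = 1.257, so power is 0.896.
- n = 23 (single arms): (0.23 − 0.2374) / 0.1163 = −0.064, so power is 0.474.

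With exact enumeration for the other two tests, at two-sided 5%:

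| Per group | z | Chi-square | Fisher |
|---|---|---|---|
| 23 | 0.474 | 0.499 | 0.377 |
| 47 | 0.784 | 0.802 | 0.719 |
| 64 | 0.896 | 0.904 | 0.865 |

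The stated 80% is thus consistent with 94 pooled over NAC, using a two-sided z or chi-square test. Single arms of 23 do not reach 80% even one-sided (0.495 to 0.622). The varenicline rate detectable with 80% power against 10%, two-sided, is 33.6% (z), 32.9% (chi-square) or 35.5% (Fisher) at 47 per group, and 29.5%, 29.3% or 30.9% at 64 per group.

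**The case against.** The strongest reply is that little depends on this. The outcome is exploratory, and the plan disclaims power for the additive effect. If 94 is right, the power sentence roughly stands; if 150 and 15% are right, power is better than stated. That is correct, and it is why the point is minor. It does not make the three numbers compatible.

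A second reply is that section C already plans for a much larger loss, so 15% may be the figure out of line. This is fair and belongs in the reconciliation. But 33% is not 37%, and 100 complete datasets exceeds 94 participants with clinical data. How the two relate depends on what a complete dataset is, which is not defined.

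A third reply is that pooling over NAC is the natural reading, given the assumption of no additive effect. I accept that. The link from the 80% to the 94 is still an inference, because neither the test nor its sidedness is stated. The fMRI calculation in the same section is 1-tailed, and a one-sided z-test would need only about 39 per group and give 0.867 at 47. Naming the test is missing detail on an exploratory outcome and not a separate fault.

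Three stronger readings are tempting, and the documents support none of them:

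- *The power is overstated.* Under 150 and 15% it is understated.
- *The primary fMRI calculation falls with the 94.* It rests on 25 per group and does not use the 94.
- *The 150 is an update of an earlier total near 110.* The arithmetic would fit, but nothing in the text says so.

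**Conclusion.** The inconsistency is real and minor. With 150 randomized and 15% attrition, about 127 participants (about 32 per arm) would provide clinical data, not 94 (23 per arm). The stated 94 corresponds to about 37% attrition, against 15% stated and 33% implied by section C. The documents do not show which figure is wrong.

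For the clinical comparison, pooled as varenicline v no varenicline, two-sided power for 10% v 33% is about 0.78 to 0.80 with 94 (z or chi-square) and about 0.87 to 0.90 with about 127 (z, chi-square or Fisher). These values assume equal allocation, pooling over NAC and a two-sided 5% test. The arithmetic contradiction needs only the plan's own totals; the per-arm figure of about 32 also assumes equal allocation.

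**What to change.** Keep 150 as the number randomized, and in section 1.d choose one of:

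1. If 15% holds, restate the number with clinical data as about 127 (about 32 per arm).
2. If 94 holds, restate attrition as about 37%, and align the total with the per-arm number (4 × 23 = 92).

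In either case, reconcile the result with the 100 complete datasets in section C and say what counts as complete. Then restate the power or the detectable rate for the chosen number. For about 127, that is two-sided power of about 0.87 to 0.90 for 10% v 33%, or 80% power for a varenicline rate of about 29% to 31%. A clause naming the pooled comparison, the test and its sidedness would let a reader check it.

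These changes are wording only and add no participants. If the sponsor finds that 150 is the wrong figure, and that about 110 or 111 were meant, that is a change of design target. Sections A.a, 1.a and C and the Targeted Enrollment Table would then all have to change along with section 1.d, and 100 complete datasets would allow a loss of only about 10% (1 − 100/110.6 = 9.6%).
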